10.9.1 Presence of Baseline Resistance-Associated Variants

For the efficacy subgroup analyses defined in Section 10.6, any NS3/4A variant and any NS5A variant are defined as follows, where baseline amino acid variants with $\geq 15\%$ prevalence at certain important signature amino acid positions are considered. Amino acid positions in NS3/4A and NS5A in genotype 2 subjects to be used in subgroup analyses are 155, 156, 168 in NS3 and 24, 28, 30, 92, 93 in NS5A (see Table 8). HCV GT2 subjects with any baseline variant at positions 155, 156, or 168 will be counted as having any NS3/4A variant at baseline. Similarly, HCV GT2 subjects with any baseline variant in positions 24, 28, 30, 92 or 93 will count as having any NS5A variant.

10.10 Patient Reported Outcomes

The following instruments will be used to collect patient reported outcomes (PROs): the EuroQol-5 Dimensions-3 Level (EQ-5D-3L)⁵ including the Visual Analog Scale (VAS) and the Fatigue Severity Scale (FSS).

The change from baseline to each applicable post-baseline timepoint in the FSS total score, EQ-5D-3L health index score and VAS score will be summarized descriptively at each visit and for change from baseline to each visit by treatment arm. For each of these scores, mean change from Baseline to Final Treatment Visit and from Baseline to Post-Treatment Week 12 will be compared between treatment arms using an analysis of covariance (ANCOVA) model with treatment arm as a factor and baseline score as a covariate.

Subject's responses to the EQ-5D-3L will be combined into a unique health state using a 5-digit code with 1 digit from each of the 5 dimensions. The EQ-5D-3L states will be converted into a single preference-weighted health utility index score by applying Japan-specific weights, if applicable. The VAS score will be analyzed separately.

The FSS consists of 9 questions using a 7-point Likert scale. A total score is calculated as the average of the individual item responses, with lower scores indicating less impact of fatigue.

Summary statistics (n, mean, SD, median, minimum and maximum) at each visit and for change from baseline to each visit will be provided for the EQ-5D-3L health index score, VAS score and FSS total score. In addition, the number and percentage of subjects who have ever experienced an increase from baseline up through each applicable time point of greater than or equal to 0.7 in the FSS total score will be computed by treatment arm, along with two-sided 95% CI calculated using the normal approximation to the binomial distribution.

For EQ-5D-3L index and VAS scores, no imputation will be performed for missing items. The missing items of the FSS questionnaire will be imputed with the average score of the answered items as long as more than 50% of the items on the FSS are answered.

If a subject starts another treatment for HCV, then all PRO values for this subject measured on or after the start date of the new HCV treatment will be excluded from analyses.

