4.2 Design Diagram

This is a Phase 3, randomized, open-label, active-control, multicenter study to evaluate the efficacy, safety and pharmacokinetics of ABT-493/ABT-530 in chronic HCV GT2-infected HCV DAA treatment-naïve Japanese adult subjects without cirrhosis. This study consists of a Treatment Period (TP) and a Post-Treatment (PT) Period.

Figure 1. Study Schematic

Approximately 120 HCV GT2-infected DAA treatment-naïve subjects (including subjects who are IFN treatment experienced with or without RBV) without cirrhosis will be enrolled into one of two treatment arms (80 subjects into Arm A and 40 subjects into Arm B)

- Arm A: ABT-493/ABT-530 300 mg/120 mg QD for 8 weeks;
- Arm B: SOF 400 mg QD plus RBV (600 – 1000 mg based on weight divided BID) for 12 weeks.

Subjects meeting all eligibility criteria will be randomized to Arms A or B. The randomization will be stratified by prior IFN-experience (naïve versus experienced) and screening HCV RNA viral load (< or ≥ 6 million IU/mL). Subjects will be randomized in a 2:1 ratio to Arms A (80 subjects) or B (40 subjects).

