10.5 Secondary Efficacy Analyses

The following secondary endpoints will be summarized:

- the percentage of subjects achieving SVR₁₂ for Arm A (the ABT-493/ABT-530 8-week regimen)
- the percentage of subjects in each treatment arm with on-treatment virologic failure (defined as confirmed increase of > 1 log₁₀ IU/mL above nadir during treatment, confirmed HCV RNA ≥ 100 IU/mL after HCV RNA < LLOQ during treatment, or HCV RNA ≥ LLOQ at the end of treatment with at least 6 weeks of treatment), and
- the percentage of subjects in each treatment arm with post-treatment relapse (defined as confirmed HCV RNA ≥ LLOQ between end of treatment and 12 weeks after the last dose of study drug among subjects who completed treatment as planned with HCV RNA < LLOQ at the end of treatment, excluding subjects who have been shown to be reinfected).

For the first secondary efficacy endpoint, the percentage of achieving SVR₁₂ in Arm A and a two-sided 95% confidence interval will be calculated using the normal approximation to the binomial distribution, unless the rate is 100% and then the Wilson's score method will be used.

The percentage of subjects with on-treatment virologic failure and post-treatment relapse will be summarized for each treatment arm. Two-sided 95% confidence intervals will be provided for rates within treatment arms and for the difference between arms (Arm A minus Arm B) using Wilson's score confidence intervals. For the analysis of relapse and reinfection, completion of treatment is defined as any subject assigned to the 12-week treatment with study drug duration of 77 days or greater; or any subject assigned to the 8-week treatment with study drug duration of 52 days or greater. Subjects with probable reinfection based on HCV sequencing or differing post-treatment HCV genotype or subtype will be summarized separately from relapse.

In addition, a summary of reason for SVR₁₂ non-response (e.g., on-treatment virologic failure, relapse, re-infection, other) will be provided for each treatment arm.

Similar secondary endpoint analyses (SVR₄ in Arm A, on-treatment virologic failure in each arm, and relapse through PT Week 4) will be performed for the interim analysis.

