10.6 Sensitivity Analyses for SVR

The following analysis approaches will be used as sensitivity analyses for evaluating SVR₁₂ rates within and between treatment arms for the primary efficacy endpoint:

- A two-sided 95% confidence interval for the SVR₁₂ rates within each arm will be calculated using a Wilson score interval.
- The percentage of subjects achieving SVR₁₂ will be compared using a logistic regression model with treatment arm as a factor, and baseline log₁₀ HCV RNA level, HCV genotype 2 subtype, and prior HCV treatment history as covariates.

- The difference in SVR₁₂ rates (Arm A minus Arm B) will be analyzed using a stratum-adjusted Mantel-Haenszel (MH) proportion with a continuity correction for variance, adjusting for both of the randomization stratum (described in Section 5.2).
- A two-sided 95% confidence interval for the difference in SVR₁₂ rates (Arm A minus Arm B) will be calculated using a Wilson score interval.

The above analyses will be performed on the ITT, and mITT-GT-VF populations, as applicable. The same sensitivity analyses will be performed for SVR₄ in the interim analysis.

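### SAP Section 10.10 leaves the randomisation factors out of the PRO ANCOVA and gives FSS worsening only per-arm normal-approximation intervals, with no interval for the arm difference

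*SAP*

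**What the plan says.** Section 4.2 sets the allocation, "80 subjects into Arm A and 40 subjects into Arm B", and the stratification: "The randomization will be stratified by prior IFN-experience (naïve versus experienced) and screening HCV RNA viral load", the viral load being cut at 6 million IU/mL. Section 5.2 repeats this.

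Section 10.10 plans one between-arm analysis of the PROs. Mean change in FSS total score, EQ-5D-3L index and VAS, from baseline to the Final Treatment Visit and to Post-Treatment Week 12, is "compared between treatment arms using an analysis of covariance (ANCOVA) model with treatment arm as a factor and baseline score as a covariate". No stratification factor appears, and no stratified sensitivity analysis of the PROs is planned.

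The same section defines a responder measure of fatigue worsening: ever having had an increase of "greater than or equal to 0.7 in the FSS total score". The number and percentage "will be computed by treatment arm, along with two-sided 95% CI calculated using the normal approximation to the binomial distribution". No difference between arms is specified, and nothing is said about an observed rate of 0% or 100%.

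Other sections treat binary outcomes differently. For on-treatment virologic failure and relapse, Section 10.5 gives intervals within arms and "for the difference between arms (Arm A minus Arm B) using Wilson's score confidence intervals". Sections 10.7 and 10.8 also use Wilson intervals within arms and for the difference. Where the plan uses the normal approximation for SVR (Sections 10.3, 10.4 and 10.5), it switches to Wilson when the rates are 100%.

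**The concern.** There are two separate weaknesses in one section.

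First, stratified randomisation balances the strata between arms, so the true variability of the arm contrast is already reduced if the strata matter. A model that omits them leaves stratum variance in the residual and reports a standard error that does not reflect the reduction. Precision provided by the design then goes unused, in a trial with only 40 controls.

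Second, the normal-approximation (Wald) interval behaves poorly for low proportions in groups of 40 and 80, and it collapses to a point when nobody worsens. The arm difference in fatigue worsening would be reported without any planned measure of uncertainty, because two separate per-arm intervals do not make an interval for a difference.

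**Working it through.** **Inputs.** From the SAP: 80 and 40 subjects, two binary stratification factors, two-sided 95% intervals. The SAP gives no power, standard deviation or event rate for any PRO, so there is no PRO figure of its own to reproduce. The share of variance explained by the strata and the FSS worsening rates below are assumptions. All 120 subjects are taken to have data.

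**(a) ANCOVA.** Let R² be the share of variance left after arm and baseline score that the two factors explain. Omitting them inflates the model standard error by about 1/√(1 − R²):

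- R² = 0: 1/√1 = 1.00
- R² = 0.02: 1/√0.98 = 1.01
- R² = 0.05: 1/√0.95 = 1.03
- R² = 0.10: 1/√0.90 = 1.05
- R² = 0.20: 1/√0.80 = 1.12

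A simulation confirms this (120 subjects, 2:1, permuted blocks within four strata, 6,000 runs; assumed prevalences 20% IFN-experienced and 35% high viral load). The ratios of mean standard errors were 1.00, 1.01, 1.03, 1.05 and 1.12. Type I error without the factors was 5.1%, 4.7%, 4.4%, 3.9% and 2.9%; with them it stayed near 5%. The Monte Carlo standard error is √(0.05 × 0.95/6000), about 0.3 points. At R² = 0, adding the factors costs essentially nothing: mean standard error 0.1938 with them, 0.1937 without.

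**(b) FSS worsening.** Exact coverage of a nominal 95% interval at true rate p is the sum, over all counts x whose interval contains p, of the Binomial(n, p) probability of x.

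| True rate (assumed) | n=40 Wald | n=40 Wilson | n=80 Wald | n=80 Wilson |
|---|---|---|---|---|
| 2% | 55.3% | 95.4% | 80.0% | 97.8% |
| 5% | 86.8% | 95.2% | 90.7% | 93.7% |
| 10% | 91.4% | 94.3% | 90.0% | 96.3% |
| 15% | 93.9% | 95.8% | 91.4% | 96.0% |
| 20% | 90.5% | 92.8% | 93.2% | 96.5% |
| 30% | 93.0% | 94.4% | 94.9% | 96.3% |

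Mean widths at n=40, Wald against Wilson: 0.121 and 0.146 at a 5% rate; 0.178 and 0.186 at 10%; 0.215 and 0.216 at 15%; 0.243 and 0.239 at 20%; 0.280 and 0.270 at 30%. Wald is clearly narrower only up to about 10%. Above that, its shortfall in coverage comes from where it is centred.

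With no events, Wald is 0% to 0%. The Wilson upper limit is z²/(n + z²): 3.84/43.84 = 8.8% for n=40 and 3.84/83.84 = 4.6% for n=80. At a true rate of 5%, no events among 40 has probability 0.95⁴⁰ = 13%.

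**(c) The missing difference.** For illustration, take 8/80 against 8/40. The Wilson limits are 5.2% to 18.5% and 10.5% to 34.8%. The difference is 10.0% − 20.0% = −10.0 points. The Wilson-score (Newcombe) limits are:

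- lower: −0.100 − √((0.100 − 0.052)² + (0.348 − 0.200)²), about −25.5 points
- upper: −0.100 + √((0.185 − 0.100)² + (0.200 − 0.105)²), about +2.8 points

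The planned output would show the −10.0 points by subtraction but not the range around it.

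**The case against.** The main PRO model follows the plan's own convention. The primary SVR12 comparison in Section 10.3 is also unadjusted; the strata enter only a sensitivity analysis (Section 10.6) and the homogeneity assessment (Section 10.6.2). The PRO model already carries the baseline score, usually the most useful covariate. Nothing in the SAP shows that IFN history or viral load predicts PRO change, and if they do the error is conservative. All of this stands, and it makes the first part an improvement in precision and not the repair of a contradiction.

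The normal approximation is likewise one of two conventions in the plan, since it serves the primary and first secondary endpoints. That also stands, but those uses have a fallback to Wilson at 100% and the FSS interval has none.

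A reader might infer that the planned intervals are simply too narrow. The widths do not support that above a rate of about 10%; coverage below nominal is the accurate description. Exact coverage is also jagged: at n=40 it is 94.4% at a true rate of 7.3%, 80.4% at 7.5% and 91.4% at 10%, because the upper limit for 1/40 lies at 7.34%. The 80.4% is a local trough and should not be taken as typical.

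A reader might also infer that the plan cannot state the difference in fatigue worsening. It can, by subtracting the two percentages; only the interval is missing. Fatigue is also compared between arms through the FSS mean-change ANCOVA.

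**Conclusion.** The point holds as a minor one. It is certain from the text that the PRO ANCOVA omits both randomisation factors, that the FSS interval has no rule for 0% or 100%, and that no interval is planned for the arm difference in FSS worsening.

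The size of the effect rests on assumptions. Standard-error inflation is 0% at R² = 0, about 3% at 5% and about 5% at 10%. To say outright that the standard errors are too large would go beyond the SAP, which gives no information on R². Coverage of the planned FSS interval is mostly below 95% at low to moderate assumed rates, worst at the lowest rates and in the arm of 40. True FSS rates are not in the SAP.

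Section 4.3 justifies the −10% margin partly by a shorter, ribavirin-free regimen. One might infer that the PROs carry that argument, but the section does not mention them. They are neither primary nor secondary endpoints in Sections 4.1, 10.3 and 10.5, no success criterion depends on them, and the primary SVR12 conclusion is untouched.

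**What to change.** In Section 10.10:

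- Fit the ANCOVA with treatment arm, prior IFN experience (naïve or experienced) and screening HCV RNA (below 6 million IU/mL, or 6 million and above) as factors, and baseline score as covariate.
- For an FSS increase of at least 0.7, replace the normal-approximation interval with a Wilson interval per arm, and add the difference, Arm A minus Arm B, with the Wilson-score interval already specified in Section 10.5.

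The cost is a change of SAP wording, two model terms (residual degrees of freedom fall from 120 − 3 = 117 to 120 − 5 = 115 with complete data) and one extra table column for the difference. No new data are needed, and the interval method is already in the plan.

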11.0 Safety Analysis

11.1 General Considerations

Safety data will be summarized for each treatment arm using the safety population. For safety analyses specified below, comparisons between the treatment arms will be performed.

11.2 Analysis of Adverse Events

Adverse events will be coded using the Medical Dictionary for Regulatory Activities (MedDRA). The actual version of the MedDRA coding dictionary will be noted in the clinical study report.

11.2.1 Treatment-Emergent Adverse Events

Treatment-emergent adverse events are defined as any adverse event (AE) with an onset date that is after the first dose of study drug and no more than 30 days after the last dose of study drug. Events where the onset date is the same as the study drug start date are assumed to be treatment-emergent. If an incomplete onset date was collected for an adverse event, the event will be assumed to be treatment-emergent, unless there is other evidence that confirms that the event was not treatment-emergent (e.g., the event end date was prior to the study drug start date).

11.2.2 Tabulations of Treatment-Emergent Adverse Events

The number and percentage of subjects in each arm with treatment-emergent adverse events will be tabulated by primary MedDRA System Organ Class (SOC) and preferred term. The system organ classes will be presented in alphabetical order, and the preferred terms will be presented in alphabetical order within each system organ class.

Adverse Event Overview

An overview of AEs will be presented for each treatment arm consisting of the number and percentage of subjects experiencing at least one event for each of the following AE categories:

- Any treatment-emergent adverse event;
- Treatment-emergent adverse events with a "reasonable possibility" of being related to study drug (ABT-493/ABT-530, SOF or RBV);
- Treatment-emergent adverse events of grade 3 or higher;
- Serious treatment-emergent adverse events;
- Serious treatment-emergent adverse events with a "reasonable possibility" of being related to study drug (ABT-493/ABT-530, SOF or RBV);
- Treatment-emergent adverse events leading to discontinuation of study drug;
- Treatment-emergent adverse events leading to discontinuation of study drug with a "reasonable possibility" of being related to study drug (ABT-493/ABT-530, SOF or RBV);
- Serious treatment-emergent adverse events leading to discontinuation of study drug;
- Treatment-emergent adverse events leading to interruption of study drug;
- Treatment-emergent adverse events of Grade 3 or higher with a "reasonable possibility" of being related to study drug (ABT-493/ABT-530, SOF or RBV);
- Treatment-emergent adverse events leading to RBV dose modification (Arm B);
- Treatment-emergent adverse events leading to death;
- Deaths.

The percentage of subjects experiencing treatment-emergent adverse events and treatment-emergent adverse events with a "reasonable possibility" of being related to study drug, and grade 3 or higher treatment-emergent adverse events will be compared between the two arms using Fisher's exact tests. Only p-values ≤ 0.100 when rounded to three digits will be presented.

Adverse Events by SOC and Preferred Term

Subjects reporting more than one AE for a given preferred term will be counted only once for that term (most severe/highest grade incident for the severity tables and most related incident for the relationship tables). Subjects reporting more than one AE within an SOC will be counted only once for that SOC. Subjects reporting more than one AE will be counted only once in the overall total.

The following summaries of AEs by SOC and preferred term will be generated by treatment arm:

- Treatment-emergent adverse events;
- Treatment-emergent adverse events with a "reasonable possibility" of being related to study drug (ABT-493/ABT-530, SOF or RBV);
- Serious treatment-emergent adverse events;
- Serious treatment-emergent adverse events with a "reasonable possibility" of being related to study drug (ABT-493/ABT-530, SOF or RBV);
- Grade 3 or higher treatment-emergent adverse events;
- Treatment-emergent adverse events leading to discontinuation of study drug;
- Treatment-emergent adverse events leading to discontinuation of study drug with a "reasonable possibility" of being related to study drug (ABT-493/ABT-530, SOF or RBV);
- Serious treatment-emergent adverse events leading to discontinuation of study drug;
- Treatment-emergent adverse events of Grade 3 or higher with a "reasonable possibility" of being related to study drug (ABT-493/ABT-530, SOF or RBV);
- Treatment-emergent adverse events leading to interruption of study drug;
- Treatment-emergent adverse events leading to RBV dose modification (Arm B only);
- Treatment-emergent adverse events leading to death.

The percentage of subjects experiencing treatment-emergent adverse events and treatment-emergent adverse events with a "reasonable possibility" of being related to study drug, and grade 3 or higher treatment-emergent adverse events will be compared between the two arms using Fisher's exact tests. Only p-values ≤ 0.100 when rounded to three digits will be presented. In addition, the number and percentage of subjects experiencing treatment-emergent adverse events and study drug related treatment-emergent adverse event ($\geq 2\%$ and ≥ 2 subjects in either Arm A or Arm B) will be tabulated according to SOC and preferred term.

A listing of treatment-emergent adverse events grouped by body system and preferred term with subject numbers will be created for each treatment arm.

Adverse Events by Preferred Term

The number and percentage of subjects experiencing treatment-emergent adverse events will be tabulated according to preferred term and sorted by overall frequency for the total number of subjects in Arm A. Similar summaries will be provided for Grade 3 or higher treatment-emergent adverse events, treatment-emergent adverse events and treatment-emergent serious adverse event related to study drug (ABT-493/ABT-530, SOF or RBV), and treatment-emergent adverse events of Grade 3 or higher with a "reasonable possibility" of being related to study drug (ABT-493/ABT-530, SOF or RBV). In addition, the number and percentage of subjects experiencing treatment-emergent adverse events and study drug related treatment-emergent adverse event ($\geq 2\%$ and ≥ 2 subjects in either Arm A or Arm B) will be tabulated according to PT and sorted by overall frequency for the total number of subjects in Arm A.

Adverse Events by Maximum Severity Grade Level

Treatment-emergent adverse events and study drug-related treatment emergent adverse events will be summarized by maximum severity grade level of each preferred term. Each adverse event will be assigned a grade level (grade 1, 2, 3, 4, or 5) by the investigator. If a subject has an AE with unknown severity, then the subject will be counted in the severity grade level category of "unknown," even if the subject has another occurrence of

the same event with a severity present. The only exception is if the subject has another occurrence of the same AE with the highest grade level (grade 5). In this case, the subject will be counted under the "Grade 5" category.

Adverse Event by Maximum Relationship

Treatment-emergent adverse events also will be summarized by maximum relationship of each preferred term to study drug (ABT-493/ABT-530, SOF or RBV), as assessed by the investigator. If a subject has an adverse event with unknown relationship, then the subject will be counted in the relationship category of "unknown," even if the subject has another occurrence of the same event with a relationship present. The only exception is if the subject has another occurrence of the same adverse event with a relationship assessment of "Reasonable Possibility." In this case, the subject will be counted under the "Reasonable Possibility" category.

Adverse Events by Subgroups

Subgroup analyses will be performed for the safety population. To evaluate the impact of various characteristics, treatment-emergent adverse events will be summarized by treatment arm for each of the following subgroups:

- Sex (male, female)
- Age (< 65 years, ≥ 65 – < 75 years, ≥ 75 years)
- BMI (< 25, ≥ 25 kg/m²)
- Baseline fibrosis stage (F0 – F1, F2, F3)
- History of cardiovascular disease (yes/no)
- History of diabetes (yes/no)
- Concomitant treatment with liver protectants (yes/no)
- Concomitant use of Proton Pump Inhibitors (PPIs) (yes/no)
- Concomitant use of Calcium Channel Blockers (CCBs) (yes/no)

For each subgroup, the adverse event overview will be prepared and the number and percentage of subjects experiencing treatment-emergent adverse events will be summarized by primary MedDRA SOC and preferred term in each treatment arm.

The Breslow-Day test will be used to examine the homogeneity of treatment effect across subgroups for each event type in the AE overview table. The Breslow-Day test will only be performed if there are at least 10 subjects per arm with an event within the subgroup.

Other Adverse Events

The number and percentage of subjects experiencing at least one treatment-emergent adverse event in the search defined below by Product MedDRA Query (PMQ) will be presented overall and by SOC and PT. In addition, a listing of treatment-emergent adverse events for subjects meeting the search criterion will be provided.

"Hepatic Decompensation and Hepatic Failure" (PMQ).

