4.0 Study Objectives, Design and Procedures

4.1 Objectives

The primary objectives of this study are to assess the efficacy and safety of 8 weeks of treatment with the combination regimen ABT-493/ABT-530 compared to 12 weeks of treatment with SOF and RBV in HCV GT2-infected Japanese adults without cirrhosis.

The secondary objectives are to assess:

[figure not shown]
- The percentage of subjects achieving SVR₁₂ for Arm A;
- The percentages of subjects with on-treatment virologic failure;
- The percentages of subjects with post-treatment relapse.

Additional objectives are to assess pharmacokinetics and emergence and persistence of viral variants in these treatment regimens.

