11.3.2 Statistical Methods

The baseline value for clinical laboratory tests will be the last available measurement on or before the day of the first dose of study drug. Values on Day 1 must also be before the time of first dose if time is available. The same baseline value will be used for change to Treatment Period visits and change to Post-Treatment Period visits.

Mean changes from baseline to each post-baseline visit, including applicable post-treatment visits, will be summarized for each treatment arm. Each protocol-specified laboratory parameter will be summarized with the sample size, baseline mean, visit mean, change from baseline mean, standard deviation, minimum, median, and maximum.

Scatterplots of baseline versus final treatment visit for each hematology and chemistry parameter (specified in [Table 9](#)) and plots of the mean change in bilirubin (total, direct and indirect) from baseline to each treatment visit by treatment arm will be produced.

The laboratory parameters defined in [Table 9](#) will be assigned a toxicity grade of 1, 2, 3, or 4. The number and percentage of subjects with a maximum toxicity post-baseline grade of 1, 2, 3 or 4 will be summarized for each treatment arm. The maximum post-baseline value must be in a toxicity grade that is more extreme than the toxicity grade corresponding to the baseline value to be counted. The summary will also include the number and percentage of subjects with a maximum of at least Grade 3 for all laboratory parameters in [Table 9](#). Comparisons of the percentage of subjects experiencing a value meeting at least Grade 2 between treatment arms will be performed using Fisher's exact tests. Only P values ≤ 0.100 when rounded to three digits will be presented. A listing of all relevant laboratory parameters will be provided for each subject who had an increase to Grade 2 or higher value for any laboratory variable in [Table 9](#).

For ALT and total bilirubin, shift tables from baseline to maximum value in toxicity grade ([Table 9](#)) during the treatment period will be created. The shift tables will cross tabulate the frequency of subjects with baseline grade (0, 1, 2, 3, or 4) versus post-baseline

maximum grade (0, 1, 2, 3, or 4). Laboratory values of ALT and total bilirubin within normal ranges are defined as Grade 0.

Table 9. Definitions of Toxicity Grades 1, 2, 3, and 4 for Laboratory Values

| Test | Grade 1 | Grade 2 | Grade 3 | Grade 4 |

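### Overall between-arm safety comparisons are Fisher p-values shown only at or below 0.100, with no difference or interval; adding these and dropping the filter is a cheap improvement

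*SAP*

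**What the plan says.** SAP 4.1 makes safety comparative and primary: the aim is "to assess the efficacy and safety of 8 weeks of treatment with the combination regimen ABT-493/ABT-530 compared to 12 weeks of treatment", the control regimen being SOF plus RBV. SAP 11.1 carries this forward: "For safety analyses specified below, comparisons between the treatment arms will be performed".

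The overall comparisons then specified are these:

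- **Adverse events (11.2.2).** The percentages with any treatment-emergent event, with a drug-related event and with an event of grade 3 or higher "will be compared between the two arms using Fisher's exact tests". The rule "Only p-values ≤ 0.100 when rounded to three digits will be presented" follows. Test and rule appear under the overview and again under the tables by system organ class and preferred term.
- **Laboratory values (11.3.2).** "Comparisons of the percentage of subjects experiencing a value meeting at least Grade 2 between treatment arms will be performed using Fisher's exact tests", followed by "Only P values ≤ 0.100 when rounded to three digits will be presented".

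Breslow-Day tests in 11.2.2 and 11.3.2 address homogeneity across subgroups, not the overall difference. Section 11 specifies no between-arm difference, ratio or confidence interval. Numbers and percentages per arm are planned for the adverse event categories and toxicity grades.

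By contrast, 10.3, 10.5, 10.7 and 10.8 give 95% intervals for efficacy differences (Arm A minus Arm B); the last three use the Wilson score method.

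**The concern.** A p-value that is blanked above 0.100 tells the reader only that it exceeded 0.100. It does not separate data that rule out a sizeable difference from data that are too sparse to tell. An interval does separate them, and the plan gives none for safety.

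This matters here for two reasons. First, safety against the control is half of the stated primary objective. Second, SAP 4.3 justifies the 10% efficacy margin partly by the possible clinical advantage of shorter treatment and no RBV. A tolerability gain is a natural part of that argument, and the plan would report it without any statement of precision. The display rule also depends on the outcome, so the p-values that reach the tables are only the small ones.

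**Working it through.** **Inputs.** Arm sizes of 80 and 40 (SAP 4.2). Two-sided Fisher's exact test, with p rounded to three digits and shown only if at or below 0.100 (SAP 11.2.2, 11.3.2). The SAP gives no safety event rates, so the rates below are assumptions.

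**The plan's own figure.** There is none for safety. The only power statement (SAP 4.3, above 80%) concerns SVR12 non-inferiority. Exact enumeration of the planned interval rule at 96% v 95% gives 87.6%, in agreement with it. It has no bearing on the safety comparisons.

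**Step 1: how often the p-value is blank.** For each pair of counts (a of 80, b of 40), compute the Fisher p-value. Then sum Bin(a; 80, pA) × Bin(b; 40, pB) over all pairs with rounded p above 0.100. Power at 0.05 is the same sum over pairs with rounded p at or below 0.05.

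| Assumed true rates, A v B | Difference (points) | Power at 0.05 | p-value blank |
|---|---|---|---|
| 10% v 2.5% | +7.5 | 17% | 64% |
| 15% v 5% | +10 | 27% | 56% |
| 20% v 10% | +10 | 23% | 66% |
| 40% v 20% | +20 | 60% | 31% |
| 5% v 15% | -10 | 40% | 49% |
| 10% v 20% | -10 | 29% | 59% |

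The range of 31% to 66% belongs to these six scenarios and is not a bound: 40% v 50%, also a 10-point difference, gives 76%.

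**Step 2: what a blank can contain.** The interval combines the Wilson limits (l, u) of each arm, which I take to be what 10.5 means by a Wilson score interval for a difference:

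- lower = d - √[(pA - lA)² + (uB - pB)²]
- upper = d + √[(uA - pA)² + (pB - lB)²]

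For 8/80 v 8/40, pA = 0.100 with Wilson limits 0.0515 and 0.1851, and pB = 0.200 with limits 0.1050 and 0.3476. The difference d is -0.100.

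- lower = -0.100 - √(0.0485² + 0.1476²) = -0.255
- upper = -0.100 + √(0.0851² + 0.0950²) = +0.028

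Three results whose p-value would not be printed:

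| Arm A v Arm B | Fisher p | Difference (95% interval), points |
|---|---|---|
| 8/80 v 8/40 | 0.157 | -10.0 (-25.5 to +2.8) |
| 40/80 v 26/40 | 0.173 | -15.0 (-31.7 to +3.8) |
| 5/80 v 0/40 | 0.168 | +6.3 (-3.2 to +13.8) |

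In these examples a blank is compatible with a difference of about 14 to 32 points in one direction. With no events among 40 in Arm B, no p-value appears until Arm A reaches 7/80 (p = 0.094).

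**The case against.** The case for leaving the plan alone is substantial, and much of it stands.

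- **The tables are not empty.** Counts and percentages per arm are printed, so the size of a difference is a subtraction away, and a reader with a calculator can recover any suppressed p-value or interval. This stands. What the plan omits is the stated precision, not the size.
- **The filter is declared in advance.** A blank has a defined meaning, p above 0.100, and is not selective reporting after the fact. This stands, but the filter still works on the outcome and conveys nothing about precision.
- **No safety hypothesis, margin or power is claimed.** SAP 4.1 says assess, so low power at 80 v 40 contradicts nothing and the absence of a safety margin is not an error. This stands. There is also no basis in the SAP for holding safety comparisons to an 80% power standard.
- **The rates are assumed.** They are, and the SAP defines no clinically relevant safety difference. It would be wrong to say that the test misses differences most of the time in general: at 40% v 20% its power is 60%.

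A reader might infer that the plan treats a blank as showing comparable safety, or that its safety assessment consists of nothing but p-values. The SAP supports neither. It attaches no conclusion to a blank. It also plans by-arm tables by grade and relationship, listings, laboratory changes, liver criteria and vital-sign findings. Misreading is a risk, not a stated rule.

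The objection does not answer one point. The plan chose to test between arms, then filtered the output, and gave no interval for a comparative primary objective, although it uses a suitable interval method for efficacy.

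**Conclusion.** The point holds as a cheap improvement in how the safety comparison is presented. The overall between-arm safety comparisons carry a p-value only when it is at or below 0.100, and never a difference with an interval. In the six assumed scenarios, with true differences of 7.5 to 20 points, the p-value would be absent in about 31% to 66% of trials. Observed results such as 8/80 v 8/40 would go unmarked although the data are compatible with a 25-point reduction or a 3-point excess in Arm A.

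The percentages depend on the assumed rates and on the planned 80 and 40 subjects being treated. The absence of a difference or interval in Section 11 depends on neither. No efficacy result, analysis population or stated decision rule is affected.

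**What to change.** In SAP 11.2.2 and 11.3.2:

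1. Present the difference in percentages (Arm A minus Arm B) with a 95% Wilson score interval, as in 10.5, for the three compared adverse event overview categories and for each laboratory parameter's at-least-Grade-2 comparison.
2. Remove the 0.100 display filter and show all p-values or none.
3. State that an absent or non-significant p-value is not evidence of comparable safety.
4. Label the intervals descriptive and unadjusted for multiplicity.

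Intervals for every system organ class and preferred term are not needed.

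The cost is SAP wording and extra columns in tables already planned, with no new data and no design change. Table 9 has 16 laboratory rows, so this means 3 + 16 = 19 intervals. Several will be wide, which shows openly how little 80 v 40 can say about uncommon events. The change makes the low power visible but does not cure it.
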